### INSPIRE Studies

We have completed 2 INSPIRE RCTs (protocols 2258 and 2605), improving feasibility and implementation of the program while refining procedures for study administration across multiple sites, personalizing approach to survivors through informatics programming, and with a change in primary outcomes to focus on adherence. In our first INSPIRE study we administered the online program targeting primary outcomes of depression, distress and fatigue, without personalized content but with a 3-group randomization including a 'standard care' control arm, the online intervention, and the online intervention plus a Problem Solving Treatment (PST) administered with 8 phone calls.[10, 128-130] Fred Hutch HCT survivors 3-18 years after HCT were eligible. Participation rate was 58% for those eligible and approached, with those age <40 years, non-white races, and >10 years after HCT less likely to enroll.[128] Once randomized to intervention, 77% logged in at least once and pages viewed did not differ by race, ethnicity, education, income, computer experience, donor type, healthcare adherence, distress or depression, but those likely to view 3+ pages of the site were more likely to be over 40 years and female. We found no efficacy for fatigue but did find important outcomes for distress and depression. For those who were impaired we found twice the rate of improved distress in those randomized to the intervention. Distress was more likely to improve in those age 40+ and in those <10 years after HCT[10]. From these results, we designed the next multicenter INSPIRE study to address shortfalls. Given the incremental improvement relative to large resource requirements to administer the 8-session PST with masters or doctoral level trained clinicians, and lack of interest in the number of sessions by many participants, we did not retain PST in the next study.

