Our most recent multicenter INSPIRE RCT (CA160684) provides a platform and infrastructure for this study. The project approached N=2653 screened survivors 2-10 years after HCT at 6 national transplant centers, and enrolled 1064 survivors using the eligibility criteria as planned for this protocol. Of these, 470 had impairments on one or more primary endpoints of depression, distress or overall HCA. Final 12-month outcomes were completed in December 2016, and analyses are in process. In examining reach of the entirely online INSPIRE program with social media, participation did not differ by ethnicity, urban/rural residence, transplant intensity, or diagnosis, but was more likely for women, allogeneic HCT recipients, and age 40-60[11]. We conclude that strategies are needed to improve reach to men, younger and older adults. We designed this intervention to better target engagement and meet the personal needs of these subgroups. Preliminary analyses of 3-month outcomes indicate efficacy of the intervention for distress in those who access the online intervention. We see no interaction of intervention arm

**FIGURE 1.** Survivorship self-management model (adapted from McCorkle and Colleagues, CA Cancer J Clin. 2011.)[1].

outcome based on sex, age, race or time since HCT. However, viewing the online site interacts significantly with randomized intervention, indicating significantly higher rate of improvement for intervention recipients who engaged.

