## 4.0 SUBJECT SELECTION

### Inclusion Criteria

- 4.1a** Received  $\geq 1$  autologous or allogeneic (related or unrelated) HCT with curative intent at a participating transplant center for a hematologic malignancy.
- 4.1b** Age 18 years of age or older at last transplant.
- 4.1c** Survival 2-5 years after last HCT when first approached for enrollment.
- 4.1d** In remission at time of study entry, may be receiving chemoprevention.
- 4.1e** Internet and email access.
- 4.1f** American and Canadian citizens, and/or those with mailing addresses in the US/Canada and/or temporarily residing anywhere outside the country (IE – military).

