## Measurement Time Points

The measures and their administration time points for three of the four assessments are listed in Table 1: baseline, 3 and 12 months. For group 1 intervention participants only, there will also be a brief orientation call for the study at 2 weeks, and an assessment at 6 weeks, that determines distress and knowledge of survivor health risks. Distress is measured on a 0-10 distress thermometer rating scale (0=no distress, 10=extreme distress) is >5, along with the first 2 items on the PHQ scored <=2 indicating low distress and depression symptoms. The distress thermometer is a widely used, validated and reliable measure of distress in cancer survivors.[144-147] Knowledge of HCT Survivor Health Risks is an 11-item screening for cardiometabolic and subsequent malignancy risks. Items are scored 0 ('my risk is higher') or 1 ('my risk is not different' or 'not sure') with a score >2 indicating inadequate knowledge of risks and eligibility for telehealth stepped care. The third criterion is whether the participant has viewed at least 3 pages of the online INSPIRE site. If any one of these 3 progress criteria are not met, intervention participants are stepped into telehealth self-management contact as described in Treatment section 7.5.1.

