For Hypothesis 1, the two primary endpoints, evaluated at the 12-month time point among the subjects identified at baseline as impaired for that particular endpoint criteria will each be compared between study arms as intent to treat analyses using standard logistic regression analyses, adjusted for cancer center and utilizing a two-sided  $\alpha=0.025$  level of significance to preserve type I error at 0.05 overall for the two primary endpoints. If other factors appear to be imbalanced between study arms, we will adjust analyses for those factors. Secondary analyses will evaluate depression alone, a PHQ-8 score  $\geq 10$  (essentially a subset of those with distress) and HCA-cancer in a similar manner as carried out for the primary endpoints. Continuous versions of the tests comprising the primary and secondary endpoints using linear regression models as well as adjusting or stratifying on engagement with the intervention (viewing at least 3 pages of the online program or completing telehealth calls) will also be carried out. Assumptions regarding normality of the outcomes will be assessed, although examination of outcomes in preliminary data suggests this is a reasonable assumption, with no significant skew in the distributions. If assumptions are not met, appropriate transformations will be implemented or alternative methods explored (e.g. non-parametric methods).

### Hypothesis 2

Characteristics of intervention arm participants at the 6-week interim assessment who require telehealth stepped care because they 1) do not meet criteria for adequate knowledge of subsequent malignancy and cardiometabolic risks, or 2) do not report improved distress, or 3) have not logged in to the online program will include those with higher depression or distress scores at baseline, more health care barriers at baseline, age 70+ years, male sex, people of color, lower income and education.

### Analysis Plan for Hypothesis 2

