Among subjects in Group 0 and Group 1 intervention arms, we will define the endpoint as a binary indicator of whether the individual required telehealth stepped care at the 6-week time point. We plan to use generalized linear models to evaluate associations between patient characteristic variables and likelihood of stepped care. Variables to be examined include age (<70 vs. 70+ years), sex, race/ethnicity (White non-Hispanic vs. Non-White or Hispanic), income ( $<\$40,000$  vs.  $\$40,000$  per year) and education (college graduate yes/no), PHQ8 depression  $>16$ , and Barriers to HCA  $> 0.45$ . The need for telehealth stepped care is not likely to be a rare event (rare being  $<10\%$ ) and thus odds ratios from a logistic regression model would not be good approximations of the relative risk (RR). Therefore, rather

	CTXD	HCA-Cardio	
Enroll/Consent/complete baseline	492	492	
T1: Eligible for specific endpoint	197	239	
3 mo. voluntary withdraw or mortality/illness (4%)	[8]	[10]	
3 mo. non-responders, able to respond at 12 mo. (15%)	[30 eligible for T4]	[36 eligible for T4]	
T3: 3 mo. completers (81%)	160	194	
T4: 12 mo. potential cohort	189	229	
12 mo. voluntary withdraw or mortality/illness (5% of T4)	[9]	[11]	
12 mo. non-responders (20% of T4)	[38]	[46]	
12 mo. completers (75% of T4, 72% of T1)	142	172	
	[71/arm]	[86/arm]	

than logistic regression we will likely use a log-link with Poisson error structure and robust sandwich variance estimates to directly estimate the more interpretable RR.[173] A multivariable model will be established using single-variable and step-up and step-down procedures with a liberal p-value for inclusion in the model ( $p<0.2$ ). Factors identified as significantly ( $p<0.05$ ) associated with the need for telehealth stepped care will be examined and based on the magnitude of the RR estimate and the prevalence of the particular patient characteristic, we will similarly examine indicators of response to the telehealth care based on continuous primary endpoints in that subgroup. This will establish a profile of types of survivors for whom modified approaches to care may be beneficial.

### Aim 3 and Plan for Aim 3

Determine resources that would be needed to sustain the intervention as a national HCT survivorship program if implemented through the CIBMTR/NMDP.

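### Aim 2 codes age only as under 70 versus 70+, so the model cannot show whether survivors under 40 need stepped care more often

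*Combined protocol and SAP*

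**What the plan says.** Aim 2 asks which intervention participants require telehealth stepped care at 6 weeks. Hypothesis 2 (Sections 12.6 and 12.7) names baseline depression or distress, health care barriers, and "age 70+ years, male sex, people of color, lower income and education". No younger group is named. The analysis plan then lists the covariates: "Variables to be examined include age (<70 vs. 70+ years), sex, race/ethnicity", followed by income, education, PHQ-8 and barriers. The model is a log-link Poisson regression with robust variance. Variables are selected at p<0.2, and factors significant at p<0.05 go forward to an analysis of response to telehealth. The stated product is a profile of survivors who may benefit from modified care.

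Eligibility (Section 4.1) starts at adulthood: "Age 18 years of age or older at last transplant".

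On age, the account of the earlier trials (Section 2.2, INSPIRE Studies) says of the first trial that "those likely to view 3+ pages of the site were more likely to be over 40 years and female" and that "Distress was more likely to improve in those age 40+ and in those <10 years after HCT". Of the later multicenter trial it concludes that "strategies are needed to improve reach to men, younger and older adults".

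On the triggers, Section 8 (Measurement Time Points) says: "The third criterion is whether the participant has viewed at least 3 pages of the online INSPIRE site". The Primary Aims (Section 3.1) and Hypothesis 2 instead speak of not having logged in, and Section 7.6 of no use of the program.

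**The concern.** The plan cites earlier evidence at both ends of the age range but models only the older end. Everyone under 40 sits in the reference level with the 40-69 group, which the protocol's evidence suggests engages best. Two consequences are possible.

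1. A raised need under 40 would have no coefficient in the Aim 2 model. It could not pass the p<0.05 step to the telehealth-response analysis, and so could not enter the profile that Aim 2 is meant to deliver.
2. If need under 40 is raised, the reference risk rises with it and the RR for 70+ shrinks. A U-shaped age pattern could then be reported as a weak age effect, or the age term could be dropped at p<0.2.

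The first follows from the coding alone. The second depends on a fact the documents do not supply.

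**Working it through.** **Plan's own figure.** None exists for Aim 2: no sample size, power, effect size, age distribution or stepped-care rate is given.

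**Step 1: what the coding can estimate.** With one indicator for 70+, a person aged 30 and a person aged 55 have the same age value. No data can produce an under-40 estimate from that term.

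**Step 2: how closely the earlier evidence matches the triggers.**

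| Stepped-care trigger | Age evidence in Section 2.2 | Match |
|---|---|---|
| Use of the site | First trial: 3+ page viewers more likely over 40 | Same threshold as Section 8; different from no log-in or no use elsewhere |
| Distress at 6 weeks (distress thermometer and two PHQ items) | First trial: distress improvement likelier at 40+ | Related, but a trial outcome rather than these items at 6 weeks |
| Knowledge of risks | None | No evidence |

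Section 2 (Background) also lists younger age as a risk factor for distress after allogeneic transplant.

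**Step 3: dilution formula.** Let R be the risk of needing stepped care at ages 40-69, let RR_young and RR_old be relative to that group, and let w = share <40 / (share <40 + share 40-69).

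- Reference risk under the plan = R × [1 + w(RR_young - 1)]
- Estimated RR for 70+ = RR_old / [1 + w(RR_young - 1)]

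The baseline risk R cancels.

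**Step 4: illustration (all inputs assumed).** Take need of 65% (<40), 45% (40-69) and 60% (70+). Then RR_young = 0.65/0.45 = 1.44 and RR_old = 0.60/0.45 = 1.33.

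| <40 | 70+ | w | Reference risk | RR for 70+ |
|---|---|---|---|---|
| 15% | 8% | 0.15/0.92 = 0.163 | 0.45 + 0.163 × 0.20 = 0.483 | 0.60/0.483 = 1.24 |
| 25% | 15% | 0.25/0.85 = 0.294 | 0.45 + 0.294 × 0.20 = 0.509 | 0.60/0.509 = 1.18 |

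The result is sensitive to need under 40. With 10% under 40, 10% aged 70+ and under-40 need of 50%, w = 0.10/0.90 = 0.111, the reference risk is 0.45 + 0.111 × 0.05 = 0.456, and the RR is 1.32. With under-40 need of 45% the RR is 1.33, so there is no dilution.

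**Step 5: power (assumed inputs).** Normal approximation for two proportions, two-sided 0.05, unadjusted. Central case: 40% need at ages 40-69, RR 1.5 for both tails, 15% under 40, 10% aged 70+. Then w = 0.15/0.90 = 0.167, the factor is 1 + 0.167 × 0.5 = 1.083, and the RR for 70+ is 1.5/1.083 = 1.38.

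The analysis plan includes the Group 0 and Group 1 intervention arms, about 492/2 = 246 if allocation is 1:1. Sections 7.6 and 8 give the 6-week assessment and calls to Group 1 only, about 305/2 = 152. Both are shown.

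| N | 70+, two levels | 70+, three levels | <40, three levels |
|---|---|---|---|
| 246 | 35% | 47% | 61% |
| 152 | 23% | 31% | 42% |

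If RR_young is 1.0, the third level costs the 70+ contrast at most about 3 percentage points of power, over shares of 10-25% under 40 and 5-15% aged 70+.

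**The case against.** The strongest defence is that the coding tests exactly the hypothesis stated. 70+ against everyone younger is a legitimate contrast, and 70+ against 40-69 is a different estimand rather than the uniquely correct one. That stands, and it is why the present contrast should still be reported.

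It is also fair that the first trial did not measure the 6-week triggers. It enrolled survivors 3-18 years after transplant, not 2-5. Its age finding on use concerns 3+ pages, whereas several sections define the trigger as no log-in or no use. Those definitions need reconciling in any case. Any one trigger suffices, so an age pattern in two of them need not carry through to the composite. The multicenter trial's remark on younger and older adults concerns reach, that is, who takes part. The present program was redesigned with those subgroups in mind. Preliminary results of that trial show no arm-by-age interaction, although that concerns treatment effect rather than who needs calls.

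A reader might infer that the plan will in fact dilute the 70+ effect, for instance by the 24-43% on the log scale that the two table rows in Step 4 imply (1 - ln 1.24/ln 1.33 and 1 - ln 1.18/ln 1.33, before rounding). The documents do not support that. It requires higher need under 40, and those percentages hold under-40 need fixed at 65%.

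A reader might also infer that need under 40 can never be seen. That goes too far. Age is collected, the covariate list is introduced non-exhaustively, and the process measures (Section 8) describe the characteristics of those requiring telehealth. None of these prespecifies an under-40 comparison.

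**Conclusion.** The point holds in a limited form. As coded, the age term gives no estimate for survivors under 40, although the protocol's own earlier evidence gives a reason to look at them. This follows from the text and needs no assumption.

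Dilution of the 70+ RR is conditional. It occurs if need is higher under 40 than at 40-69, by the factor in Step 3, and not otherwise. With the assumed inputs of Step 4, a true RR of 1.33 appears as about 1.18 to 1.33. The documents cannot narrow that range.

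Recoding would not make the 70+ comparison well powered. In the central case power is 47% at best, and the main limit is the probably small 70+ group. The gain is an estimate for younger survivors and a cleaner reference, in an exploratory aim whose purpose is a profile. Aim 1 is unaffected.

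**What to change.** In the analysis plan for Hypothesis 2 (Section 12.7), replace the two-level age variable with <40, 40-69 (reference) and 70+, or with a prespecified continuous non-linear term such as a restricted cubic spline. Keep the hypothesised 70+ effect, now against 40-69, and also report 70+ versus <70 as the plan now has it, so that the stated contrast remains available. Label the under-40 contrast as exploratory, or add it to Hypothesis 2.

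The three-level version costs a change of wording, one extra degree of freedom and a slightly wider interval for 70+. No new data are needed, because age is already collected at baseline.

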### Secondary Analyses

Secondary endpoints will include depression, process measures describing internet study reach and utilization, as well as outcomes of knowledge of survivorship needs. We will compare secondary outcomes knowledge of health care needs between study arms using similar analytic methods as for the primary outcomes (both binary and continuous outcomes). We will also carry out subset analyses within stratum defined by the degree of utilization of the resources (i.e. more than one page viewed of internet site – see below for alternate definitions), and receipt of the phone calls if designated, to evaluate whether, among “users”, the tailored intervention has stronger effects.

Further analyses will identify risk factors for disparities in survivorship HCA in HCT survivors. Study reach, adoption and attrition process measures will be reported descriptively.

Primary analyses will be based on 12 month outcome measurements, but we will utilize the 3 month time point in secondary longitudinal analyses modeled after those carried out in DuHamel et al.[30] Additional secondary analyses will include evaluation of the impact of the internet intervention on continuous versions of the primary endpoints, but among all participants randomized, including those not meeting criteria for inclusion in primary analyses. This will provide estimates of the impact of study intervention on an unscreened population which would be a likely dissemination methodology.

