## 8.0 EVALUATION

Table 1. PRO Measures and schedule of administration (T2 for intervention-only participants described in section 8.1)

8.1 Patient Reported Outcome Measures	T1 Baseline Screening	T3 3 month Outcome	T4 12 month Outcome
Primary Outcomes			
Cancer and Treatment Distress (CTXD)	X	X	X
Health Care Adherence (HCA)	X		X
Secondary Outcomes			
Patient Health Questionnaire-8 Depression (PHQ8)	X	X	X
Moderators and Risk Factors			
Computer and Mobile Phone Use	X		
Background: potential barriers to PCA (age, income, rural/urban, gender, cancer and treatment history, current medical history, medications)	X		
GVHD Symptom Scale (allogeneic only)	X		
Medical Comorbidities and Medications	X		X
Mediators			
Knowledge of Survivorship Needs	X	X	X
Health Self-Efficacy	X	X	X
Study Evaluation			
Evaluation of Program and Participation			X
ESTIMATED TIME REQUIRED	30-40	10-15	25-35

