## Mediators for Primary Outcomes

Knowledge of Health Care Needs. This 15-item measure addresses 2 factors: 1) knowledge of treatment and related risks, including cardiometabolic and second cancer risks, and 2) understanding of health care recommendations and emotional health resources after HCT as included in our intervention. With N=936 participants in our previous INSPIRE study, alpha is strong for the overall score ( $\alpha = .92$ ) and factors ( $\alpha = .82$ ,  $\alpha = .93$ ). The measure is derived from a similar measure developed in our SCOEN collaborations.[82]

Health Related Self-Efficacy. This measure reflects beliefs about health-related self-efficacy.[169, 170] In testing with N=860 HCT survivors, the measure has reliability of  $\alpha = 0.86$ .

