## Endpoints

The primary endpoints to be evaluated for the above hypotheses are CTXD (distress) and HCA-cardio. The primary and secondary endpoints for the study will be defined as binary outcomes. Participants will qualify for analysis of a particular endpoint if they meet eligibility at their baseline response for that endpoint (CTXD  $\geq 0.9$  or HCA-cardio  $<80\%$  [primary endpoints], or HCA-cancer  $<80\%$  [secondary endpoint], PHQ-8 score  $\geq 10$ ). Some participants will contribute to both primary endpoint analyses, and others to none or one. Similar conditional analyses will be carried out for the secondary endpoints. Stepped-care telehealth will be introduced based on PRO assessed at 6-weeks, then short term outcomes will be assessed after 3 months and delayed or sustained effects will be assessed at 1 year.

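### The binary knowledge comparison in section 12.8 has no cut-point or baseline criterion and cannot be run as written; the continuous 12-month score should be the main analysis

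*Combined protocol and SAP*

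**What the plan says.** Section 12.8 (Secondary Analyses) lists among the secondary endpoints "as well as outcomes of knowledge of survivorship needs". It says the arms will be compared on "knowledge of health care needs between study arms using similar analytic methods as for the primary outcomes (both binary and continuous outcomes".

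Section 12.4 (Endpoints) sets the general rules. Primary and secondary endpoints are binary, and "Participants will qualify for analysis of a particular endpoint if they meet eligibility at their baseline response for that endpoint". The qualifying values listed are CTXD at least 0.9, HCA-cardio below 80%, HCA-cancer below 80% and PHQ-8 at least 10. Knowledge is not on the list, although the section adds that secondary endpoints get similar conditional analyses.

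Section 8.2 (Mediators for Primary Outcomes) describes the instrument: "This 15-item measure addresses 2 factors: 1) knowledge of treatment and related risks, including cardiometabolic and second cancer risks", the second factor being understanding of recommendations and resources. It reports reliability only ("With N=936 participants in our previous INSPIRE study, alpha is strong for the overall score": .92, and .82 and .93 for the factors). No scoring direction, threshold or responder definition is given. Table 1 schedules "Knowledge of Survivorship Needs" at baseline, 3 months and 12 months without restriction by arm, and files it under mediators.

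The Measurement Time Points text in section 8.1 describes another instrument, an 11-item screen of risk knowledge at 6 weeks for Group 1 intervention participants, "with a score >2 indicating inadequate knowledge of risks and eligibility for telehealth stepped care".

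**The concern.** The primary-outcome method uses a threshold twice: at baseline to decide who is analysed, and at 12 months to decide who succeeded. For knowledge neither threshold exists. The one knowledge cut-point in the documents looks as though it could be borrowed, but it is on a different instrument, at a different time, without control data.

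Knowledge is a named secondary outcome (sections 3.2 and 12.8) and something the intervention is meant to change, so a between-arm claim is likely to be reported. If the cut-point and analysis set stay open until outcomes are available, a reader cannot tell whether a reported difference reflects the intervention or the choice of cut. Dichotomising also costs power on a score that is collected in full at three time points.

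**Working it through.** **1. What the binary analysis needs, and what is given**

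| Requirement | CTXD, HCA-cardio, HCA-cancer, PHQ-8 | 15-item knowledge measure |
|---|---|---|
| Baseline criterion (who is analysed) | Stated in 12.4 | None |
| Threshold for 12-month success | CTXD below 0.9 and HCA-cardio at least 80% stated for Hypothesis 1; the two secondaries handled similarly | None |
| Assessed in both arms | Yes (Table 1) | Yes (Table 1, no restriction by arm) |

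The 11-item screen does not fill the gap. Table 1 does not list it at baseline or 12 months. Section 8.1 gives it to Group 1 intervention participants only. The Hypothesis 2 analysis plan instead defines the 6-week stepped-care indicator in the Group 0 and Group 1 intervention arms. Those two statements need reconciling, but on either reading controls have no score.

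**2. Is there a figure in the plan to reproduce?** None for knowledge: no sample size, power or alpha is stated. The nearest figures are for the continuous primaries at two-sided 0.025. With 71 per arm and an effect of 0.52, power is 80.4%; with 86 per arm and 0.47, it is 80.0% (normal approximation). Both agree with the stated 80% but say nothing about knowledge.

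**3. Number available.** Table 3 projects 72% completing 12 months. Applying that to all 492 randomised (an assumption, since Table 3 applies it to the endpoint-eligible subsets): 492 × 0.72 = 354, or 177 per arm.

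**4. False positives if the cut is chosen after seeing outcomes.** Simulated with no true effect, 177 per arm, nominal two-sided 5%, taking the most favourable cut in all participants:

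| Assumption about the score | One fixed cut | Best of 3 | Best of 5 |
|---|---|---|---|
| Normal score, widely spaced cuts (quartiles; 10% to 90%) | about 5.5% | about 13% | about 19% |
| Normal score, closely spaced cuts (40/50/60%; 30% to 70%) | as above | 9% to 10% | about 14% |
| 15 yes/no items, reliability .92, adjacent cuts | about 5% | about 9% | about 12% |

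So cut choice alone gives about 9% to 20%. If the analyst may also choose between all randomised participants and those below the cut at baseline, the 15-item simulation gives about 15% for 3 cuts and 22% for 5 (assumed baseline-to-12-month latent correlation 0.6).

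**5. Power at an assumed effect of 0.3 SD, 177 per arm, two-sided 5%**

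- Continuous, unadjusted: Φ(0.3 × √(177/2) − 1.96) = Φ(2.82 − 1.96) = 81%.
- Continuous, adjusted for baseline with correlation r: Φ(2.82/√(1 − r²) − 1.96). For r = 0.3, 0.5 and 0.7 the first term is 2.96, 3.26 and 3.95, giving 84%, 90% and 98%.
- Median split, everyone, unadjusted: success proportions Φ(±0.15) = 0.560 and 0.440, giving 61%. Adding the baseline score to the logistic model (r = 0.5) raises this to about 72%.
- Median split in the lower half at baseline: about 41% at r = 0.5. A calculation that only halves the sample gives 35%, but it ignores the narrower outcome spread in the selected half.

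**The case against.** A reader might infer that the threshold must be taken from the trial's own outcomes. The documents do not say so; they leave it unstated. Data on 936 earlier respondents exist, and baseline scores arrive before 12-month scores, so a cut-point could be fixed in advance. The inflation in step 4 is therefore conditional on a late choice.

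A reader might also infer that the knowledge outcome as a whole cannot be analysed, or that most of its power is thrown away. That goes too far: section 12.8 already plans a continuous comparison beside the binary one, and only the binary version is blocked. Like for like, the continuous score has 81% against 61% unadjusted, and about 90% against 72% adjusted at r = 0.5. Part of the gap between the best and worst figures comes from the covariate and not from dichotomising.

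Nor do the documents prove that a baseline-impaired subset is required for knowledge. Section 12.8 asks for similar methods, not the same population, and the list in 12.4 omits knowledge, while the general sentence in 12.4 points the other way. This is an ambiguity, and it touches the continuous comparison too: the all-randomised analysis in 12.8 is written for continuous versions of the primary endpoints.

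Finally, knowledge carries no allocated alpha, Table 1 calls it a mediator, and section 8.1 says the measure is still being tested. All of this limits the weight of the point. It does not supply the missing definitions.

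**Conclusion.** The binary knowledge comparison cannot be run from the plan as written, because the 15-item measure has no cut-point and no baseline criterion, and the 11-item screen cannot stand in for it. The analysis set is unclear for both versions. If the open choices were made after outcomes are seen, a nominal 5% test would have about 9% to 20% false positives for the best of 3 to 5 cuts, and up to about 22% if the analysis set were also free. The power figures rest on assumptions not in the documents: 0.3 SD, a 5% level, 72% retention in all randomised participants, and baseline correlations of 0.3 to 0.7. The primary conclusions are unaffected. The point also assumes that Table 1's survivorship-needs measure and the health-care-needs measure of sections 8.2 and 12.8 are the same instrument.

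**What to change.** - **Section 12.8:** make the main knowledge comparison the continuous 15-item score at 12 months in all randomised participants, by linear regression with the baseline score and cancer center as covariates and the same missing-data handling as the primaries. State the scoring direction.
- **Binary version:** drop it or report it descriptively, unless a cut-point and analysis set are fixed before outcome data are examined.
- **Section 12.4:** exempt knowledge from the binary rule and the baseline-impairment rule. Editing 12.8 alone would leave the two sections in conflict.
- **Section 8.1:** state that the 11-item 6-week screen is not used for comparisons between arms.
- **Naming:** use one name for the 15-item measure throughout.

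The cost is a few sentences in three places and no new data, since the score is already scheduled at baseline, 3 and 12 months. The downside is that there is no formal test of the percentage judged knowledgeable.
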